We aim to assess the feasibility of conducting a definitive trial of interventions for adolescents with first episode psychosis (FEP). We will conduct a 3-arm pilot randomised controlled trial to determine the feasibility of comparing i) antipsychotics (APs) to ii) psychological intervention (PI) and iii) a combined treatment (APs plus PI), in 90 adolescents (aged 14-18) with FEP in NHS services in 4 sites. Randomisation will use randomised-permuted blocks of randomly varying size. Assessors will be masked to allocated treatment. PI consists of Cognitive Behaviour Therapy (CBT) plus family intervention (FI), and allows an individualised approach within clear boundaries, with specific interventions being dependent on an individual formulation (the range of permissible interventions is described in our published manuals (1-3)). Up to 30 sessions of CBT will be delivered over 6 months. FI involves an extra 6 sessions with parents to complement the CBT (as well as regular communication with parents following CBT sessions), improving communication, problem solving and reducing stress. Comparator conditions are APs alone and a combined treatment (APs plus PI). APs will be chosen from those commonly used in the treatment of adolescents and recommended in the recent NICE guidelines, with choice of individual drug made by the managing psychiatrist. Our objectives are to assess feasibility of a definitive trial, including numbers, proportions and characteristics of eligible Adolescents referred by clinicians and adolescents willing to participate, participants who drop out and participants who receive and comply with their allocated intervention. Therapeutic improvement will be assessed in terms of overall symptom severity, but also using broader, clinically relevant outcome measures of social function and target symptoms as well as overall health status and utility. Assessors blind to and independent from randomised treatment group allocation will conduct all assessments at baseline, 3, 6 (immediately post the end of treatment) and 12 months (6 months' followup after the end of treatment). In the event of a hospital admission, suicidal or dangerous ideation representing immediate risk, or deterioration at the 3-month assessment, monotherapy participants will be offered transfer to the AP+PI arm. We will also conduct a nested qualitative interview study with a purposive sub-sample of adolescents (n=15-20), parents (n=15-20) and clinicians (n=15-20) to understand experiences and acceptability of interventions and research procedures, which will further inform a definitive trial. We will also evaluate the suitability of outcome measures to assess effectiveness, safety, and acceptability. The 2-year trial will have a recruitment window of 15 months, requiring 1.5 participants per site per month (90 in total); our trial of CBT vs APs vs both in adults is currently recruiting 3 participants per month in a single site, so this is realistic despite lower incidence in adolescents). The proposed sample size is adequate for obtaining reliable parameter estimates for sample size estimates for the definitive trial, and demonstrating the feasibility of such a definitive trial. Our team includes expertise in conducting clinical trials of complex interventions, PI for psychosis, psychopharmacology, mental health in adolescents, nested qualitative research and carer and service user involvement. Five applicants were on the NICE guideline development group for CG155 (5).

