Single blind – assessors will be blind to treatment condition. Blindness will be maintained using a wide range of measures which we have implemented successfully in other single blind trials (EDIE 2; ACTION; FOCUS). These include separate offices for the therapists and research assistants, protocols for answering telephones including reminders for clinicians, participants and family members about the blind, protocols for message taking and secretarial support, separate diaries and pigeon holes and data file security, using passwords and encryption of randomisation information. We will develop a standard operating procedure (SOP) for maintaining, recording and managing blinding, which will outline all of these procedures. This SOP will be reviewed by, and agreed with, our data monitoring committee (DMC)/ trial steering committee (TSC). Each researcher will sign this SOP to confirm they understand and will comply with the blinding procedures. All blind breaks will be recorded by the trial manager and reviewed by the Chief Investigator for patterns in unblindings. There is only one follow-up scheduled during the intervention window (at 3 months). This will reduce the risk of blind breaks occurring because of therapists and RAs crossing paths for visits and it will reduce the opportunity for unblinding to occur because of communication with participants to arrange visits. Maintaining rater blindness to treatment allocation is crucial, and the DMC and TSC will regularly monitor unblindings by each centre, and implement corrective action if necessary. Following eligibility assessment and completion of baseline assessments, participants will be allocated to treatment groups through our web-based randomisation service and the Trial administrator will inform the participants of this decision. All letters to participants and clinicians will contain a standardised statement about the need to maintain the single blinding process. Any accidental unblindings will be recorded. Where possible, we will identify an independent assessor with whom the blind has not been broken to complete subsequent follow-ups, subject to any threats to participant engagement with follow-up. Given each intervention is provided in two arms of this three-arm trial, the blind will also be easier to maintain than in our previous two-arm trials.

Concomitant therapy

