CBT allows an individualised approach within clear boundaries, and incorporates a process of assessment and psychological formulation of problems and goals. The latter is standardised in a manual of agreed components. The specific interventions are dependent on the individual formulation, which focuses on development and maintenance factors, but within a range of permissible interventions described in our published manuals (1-3). Up to 30 sessions will be delivered over the 6-month treatment envelope. Fidelity to the protocol will be ensured by regular supervision and rating recordings of sessions. The overall aims of CBT will be to reduce distress (particularly that associated with psychotic symptoms) and improve quality of life. It is a collaborative therapy that works with the problems and goals that are agreed between patient and therapist. Thus, treatment targets often include positive symptoms, but frequently also include social issues such as improving relationships, maintaining functioning or developing meaningful social roles and issues of comorbidity including anxiety and depression. If comorbidity includes problematic drug or alcohol use, this can also be prioritised. The CBT will be phased as follows: i) assessment, engagement and formulation of problems and goals. Goals could include managing distress and uncertainty, allow for more intense/frequent contact and allow strategies to reassure, calm and activate individuals ii) the use of change strategies derived from the formulation to work towards the particular goals of the individual, including reduction of acute distress iii) a historical formulation phase that focuses on vulnerability factors that led to the development of FEP and includes work on selfesteem and iv) final consolidation phase focusing on staying well and relapse prevention. We have used this approach in previous trials with young people with psychosis (EDIE-2 (22) and

ACTION (17)), and younger age was a predictor of better outcomes in both trials, suggesting it is particularly well-suited to younger participants (the latter trial is particularly relevant as it specifically targeted people who were not taking APs).

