The family intervention will include psychoeducation, skills building and problem solving components. Sessions will also focus on assessment, formulation, goal setting and communication styles. The six sessions of family intervention will be delivered in tandem with individual CBT and delivered by the same therapist to maintain engagement and consistency of approach. The first FI session will occur within two weeks of randomisation and will focus on reassuring relatives by providing recovery-orientated information, managing uncertainty and distress, discussing confidentiality, assessing the parents' understanding and appraisals of the presenting difficulties and engaging the family in the therapy process. Sessions 2-5 will focus on the (i) development and sharing of emerging psychological formulations, (ii) providing recovery-orientated information to combat stigma and pessimism and (iii) developing new ways of responding to difficulties when they emerge (including promoting personal strengths and reinforcing existing beneficial strategies). These sessions will be scheduled throughout the therapy window to match the pacing and content of the individual CBT sessions and the concerns of family members. Therapists will be flexible with the order that these tasks are covered and adapt the process to the needs and priorities of the parents/carers as long as this does not conflict with the interests of the participant. The final parent/carer session will occur within four weeks of the client finishing CBT. The aim of this final session is to make the family active stakeholders in the client's staying well plans. Ideally both parent/carer and client will be present. All parties will review the formulation, and discuss ways of consolidating the strategies learned during therapy, providing a summary of useful strategies and developing monitoring and action plan for future difficulties.

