Greater Manchester Mental Health Foundation Trust will be the primary sponsor. In accordance with high standards of research governance we would ensure researchers receive training in the International Conference on Harmonisation (ICH) Guidelines - Good Clinical Practice before recruitment commences. We will set up a Trial Steering Group (TSC) and an Independent Data Monitoring and Ethics Committee (IDMC) prior to the start of the study. The TSC will comprise study applicants, a representative of the HTA, and representatives of service users and providers, and have an independent chairman. It will meet annually, and initially before the trial begins for approval of the protocol and standard operating procedures. The TSC will monitor and supervise progress, consider reports and recommendations. An observer from the HTA will be invited to all meetings. An IDMC will also be established to monitor (1) recruitment of study participants, (2) ethical issues of consent, (3) quality of data (including missing data), (4) the incidence of adverse events, and (5) any other factors that might compromise the progress and satisfactory completion of the trial. This will also have an independent chairman, and include an independent statistician. It will meet on a 6-monthly basis. An evaluation committee (all applicants and at least one independent member of the DMC) will be responsible for the consistency of recruitment, assessments and intervention.

Communication within and between sites

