Information will be age-appropriate for those still at school. Regarding assessment, it should be noted that the time use assessment assesses activity i.e. school or education attendance not simply registration. The aim for participants at school would often be to improve school or education attendance.

Assessment of safety

The following will be considered as adverse incidents; all deaths, suicide attempts, serious violent incidents, admissions to secure units, formal complaints about treatment. We plan to scrutinise any instances of participants being admitted to psychiatric hospital in the period of the trial. These events are likely to come to the attention of the therapists or assessors; however, we will also check medical notes at the end of the participants' time in the trial. The responsible clinical team, the trial management committee and the data monitoring and ethics committee (IDMC) will be informed of any adverse incidents. The response to an adverse incident will be determined on a case by case basis.

Procedures for deterioration

Participants allocated to the PI or Antipsychotic monotherapy arms and whose mental state deteriorates during the course of the study will be offered the option to move into the combined treatment arm and PI or APs will be commenced. Participants will remain in the RCT and continue to follow the schedule of assessments. Participants will be moved into the combined treatment arm if:

- They are subject to involuntary hospitalisation due to a deterioration in mental state
- There is a >12.5% deterioration in PANSS scores at the 3-month assessment.

If >12.5% deterioration in PANSS scores at the 3-month assessment is observed, the client's responsible clinician will be informed.

Informing potential trial participants about known risks and benefits

PI and APs are recommended interventions for adolescents with FEP (44). The investigators have considerable experience of administering the assessments and rating scales included in this study, and are not aware of any risks to participants. During assessment and testing, breaks will be provided to minimise possible fatigue or stress, and if indicated, can be spread over several days. Known adverse effects of APs will be described in advance.

Obtaining informed consent

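### During treatment, adverse incidents are likely to be found earlier and more often in the two therapy arms than in AP alone, so interim counts can differ without a true difference

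*Protocol*

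**What the plan says.** The protocol's *Assessment of safety* section lists the incidents of interest (deaths, suicide attempts, serious violence, secure admissions, formal complaints). On how they are found it says: "These events are likely to come to the attention of the therapists or assessors; however, we will also check medical notes at the end" of each participant's involvement. On who is told: "The responsible clinical team, the trial management committee and the data monitoring and ethics committee (IDMC) will be informed of any adverse incidents". It gives no time limit, and no route by which the NHS clinical team reports an incident to the trial.

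Therapist contact is described under *Health technologies being assessed*: "Up to 30 sessions will be delivered over the 6-month treatment envelope", and "The six sessions of family intervention will be delivered in tandem with individual CBT and delivered by the same therapist". Under *Randomisation*, participants without regular family contact do not receive the family component. *Protection against bias* observes, "Given each intervention is provided in two arms of this three-arm trial", so trial therapists serve PI and AP+PI only. In AP alone, the treating psychiatrist prescribes.

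Assessors see all arms on one schedule (*Data collection*): 3 and 6 months, and 12 months for those recruited in the first 10 months. *Protection against bias* notes that only the 3-month visit falls inside the intervention period.

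Under *Project management*, the IDMC's remit includes the incidence of adverse events. On its timing: "It will meet on a 6-monthly basis".

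**The concern.** During treatment, two of the three arms have a trial therapist who may see the participant about weekly. The third has two assessor visits. The notes check, which covers every arm, comes only when the participant leaves the trial. With equal true rates, the therapy arms would tend to show more incidents at any interim date because they are observed more closely. AP alone would look safer than it is, and a real excess there would surface later.

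What is at stake is the IDMC's interim view of incidents by arm. *Aims and objectives* also includes testing whether the safety measures suit a definitive trial. An ascertainment method that differs by arm could be carried into that trial, where the question may be whether PI is non-inferior to APs.

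**Working it through.** The protocol gives no figure on this point, so there is none to reproduce. The delay follows from its contact schedule.

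**Inputs from the protocol**
- Therapy arms: up to 30 CBT sessions in 6 months. The low case is 6 sessions, the threshold for adherent therapy under *Measurement of feasibility success criteria*.
- AP alone: assessor visits at 3 and 6 months.
- IDMC meetings every 6 months.

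**Assumptions, not in the protocol**
- Events fall evenly over months 0 to 6.
- Contacts are evenly spaced, and each event is found at the next one.
- IDMC dates are unrelated to event dates.

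**Formulas.** With contacts *d* months apart, mean delay = *d*/2. The chance that the delay carries an event past the next meeting = mean delay / 6.

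| Arm and contact | *d* (months) | Mean delay (months) | Misses next meeting |
|---|---|---|---|
| PI or AP+PI, 30 sessions | 6/30 = 0.2 | 0.1 | 0.1/6 = 1.7% |
| PI or AP+PI, 6 sessions | 6/6 = 1 | 0.5 | 0.5/6 = 8.3% |
| AP alone, two visits | 3 | 1.5 (maximum 3) | 1.5/6 = 25% |

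Family sessions are left out; counting them would shorten the therapy-arm delay a little.

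**If AP-alone visits find an event only with probability *p*, and the end notes check finds the rest**
- 6-month participants: 1.5 + ½(1−*p*)×3. This gives 1.8 months at *p* = 0.8 and 2.25 at *p* = 0.5.
- 12-month participants: 1.5 + ½[*p*(1−*p*)×3 + (1−*p*)²×9] + ½(1−*p*)×6.
  - *p* = 0.8: 1.5 + 0.42 + 0.60 = 2.52 months.
  - *p* = 0.5: 1.5 + 1.5 + 1.5 = 4.5 months.

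**Months 6 to 12.** CBT has ended in every arm. The next contact is the 12-month visit, so the mean delay is 6/2 = 3 months in all arms and the difference disappears.

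**Final counts, by illustration only.** Assume 6 true events among 30 in each arm, running detection of 90% with a therapist and 50% (range 30% to 70%) without, and an end notes check that finds 80% of the remainder.
- Before the notes check: 6×0.9 = 5.4 against 6×0.5 = 3.0 (range 1.8 to 4.2). The ratio is 1.8 (range 0.9/0.7 = 1.3 to 0.9/0.3 = 3.0).
- After it: 5.4 + 0.8×0.6 = 5.88 against 3.0 + 0.8×3.0 = 5.4 (range 1.8 + 0.8×4.2 = 5.16 to 4.2 + 0.8×1.8 = 5.64).
- The gap falls from 2.4 events to about 0.5.

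**The case against.** Several safeguards cover all arms. Assessors follow one schedule, with a wellbeing call after assessments. Admissions and SAEs are measured in every group, SAEs whether or not related. A service-use questionnaire is completed at each visit, and the end notes check applies to everyone. A reader might infer that AP-alone events could go unseen altogether, but the protocol does not support that. A complete miss needs an event that is neither disclosed at a visit nor written in the notes.

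A reader might also infer that events told only to a therapist never reach the notes and so distort the final table. But the clinical team is to be told of any incident, so such events should tend to be recorded. This cuts both ways: notes that contain therapist-relayed events are not a fully arm-neutral source.

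Other channels exist: weekly site meetings with local clinicians, contact with schools, and the offer of transfer to combined treatment after an admission, which requires the trial to know of it. None is described as an incident-reporting route with a schedule, so they soften the difference without removing it.

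A third tempting reading is that a biased harms table decides whether the definitive trial proceeds. The four progression criteria concern recruitment, retention and delivery of PI and AP. *Secondary outcomes* disclaims conclusions on safety, and no between-arm comparison or stopping rule is stated. What stands is that the IDMC does monitor incidence.

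Finally, two missed IDMC meetings is an extreme. It needs a 12-month participant whose earlier visits all fail to find the event. On the simple assumptions, 75% of AP-alone events still reach the same meeting. The 30 and 6 sessions are also ceilings; the low case above allows for sparse CBT attendance.

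**Conclusion.** The concern holds in limited form. As written, detection in months 0 to 6 is likely to be earlier and more frequent in PI and AP+PI than in AP alone, so interim counts can be higher in the therapy arms without a true difference. The mean delay is about 0.1 to 0.5 month against 1.5 months, and about 2% to 8% of events against 25% miss the next IDMC meeting. These figures assume evenly spread events and detection at the next scheduled contact; missed or unproductive AP-alone visits would lengthen that arm's delay. No claim is made that AP-alone events escape detection altogether. Final counts are much less affected, and the illustration of about half an event per arm rests wholly on assumed rates.

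**What to change.** In *Assessment of safety*:

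1. Use the same structured adverse-incident and SAE enquiry in all three arms at the existing 3-, 6- and (where offered) 12-month visits.
2. Record the source and detection date of each event (scheduled assessment; notes or clinical team; therapist), and whether a notes entry originated from a therapist report. Record every source that identifies the event, not only the first. Otherwise, events a therapist heard of first would drop out of the common-source count and bias it the other way.
3. In IDMC reports and the final harms table, base between-arm comparisons on sources common to all arms. List therapist-originated reports separately, with all events still reported.

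The cost is an extra source-and-date field on the incident form and slightly more tabulation. A therapist source reveals allocation to a therapy arm, so the field should be kept from blinded assessors.

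A notes check in all arms before each IDMC report is desirable where existing unblinded staff can do it, but not essential. It may need extra staff time at four sites, because *Concomitant therapy* gives records screening to the research assistants, who are blinded, at the end of the study.

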As this is a feasibility trial, a single primary outcome is not meaningful and the key outcomes to inform a future trial are referral rates, recruitment, attendance at therapy sessions, compliance with medication and follow-up and questionnaire response rates. Acceptability of treatment will be measured using rates of drop-out from treatment.

Secondary outcomes:

All secondary outcomes are being collected to determine their suitability for use in a subsequent trial, rather than to draw conclusions about safety or efficacy of treatments.

The proposed primary outcome measure for a subsequent definitive trial will be total PANSS score (4), a commonly used outcome in psychosis trials, allowing comparison with wider evidence. The PANSS is a 30-item rating scale designed to provide a comprehensive assessment of psychopathology in adults with a diagnosis of schizophrenia. Five components have been reported: positive, negative, depression-anxiety, agitation-excitement, and disorganisation.

In order to test the acceptability and usefulness of potential secondary outcome measures in a trial context, we will also assess: i) social/educational/occupational functioning ii) self-rated

recovery iii) dimensions of psychotic symptoms. Adverse effects (weight gain, sexual dysfunction, metabolic effects and extrapyramidal effects) will be systematically assessed. Hospital admissions, serious adverse events and dose of APs and PIs will also be measured in all groups

Social/educational/occupational functioning

Social and educational/occupational functioning will be assessed using the First Episode Social Functioning Scale (FESFS) (28). The FESFS was developed with over 200 individuals receiving services in first episode psychosis clinics. Subscales include: Friendships and social activities, Independent living skills, Interacting with people, Family, Intimacy, Relationships and social activities at work, Work abilities, Relationships and social activities at school, Educational abilities. This measure has good reliability, convergent and discriminant validity and sensitivity to change. We will also assess time use in constructive economic activity.

Recovery

Recovery will be assessed using the questionnaire about the process of recovery, a user-defined measure (QPR (29)), which is a 15-item questionnaire developed collaboratively with service users with psychosis, measuring subjective recovery.

Dimensions of Psychotic Experiences

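### The rule for transferring monotherapy participants to the combined arm is stated inconsistently, and its 12.5% PANSS trigger has no stated formula

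*Protocol*

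**What the plan says.** The Summary of Research gives the triggers as "In the event of a hospital admission, suicidal or dangerous ideation representing immediate risk, or deterioration at the 3-month assessment" and the consequence as "monotherapy participants will be offered transfer to the AP+PI arm". It sets no threshold for deterioration.

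Procedures for deterioration opens with a general provision. Participants in either monotherapy arm whose mental state worsens at any point in the study "will be offered the option to move into the combined treatment arm and PI or APs will be commenced". It then changes verb: "Participants will be moved into the combined treatment arm if" introduces a list of two events. The first is "They are subject to involuntary hospitalisation due to a deterioration in mental state". The second is "There is a >12.5% deterioration in PANSS scores at the 3-month assessment". The section adds that the responsible clinician is told when the PANSS limit is exceeded, and that participants stay in the trial and keep to the assessment schedule.

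On the instrument, the section on secondary outcomes says "The PANSS is a 30-item rating scale". It names the total score as the proposed primary outcome of a later definitive trial. It does not give the range of an item, and it says nothing about the transfer trigger.

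**The concern.** Transfer is the protocol's explicit route by which someone randomised to PI alone or AP alone receives the other trial treatment. Staff need to know which events set it in motion and whether the participant is being offered a choice or reassigned. On both points the two sections differ, and Procedures for deterioration also differs from itself.

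The 3-month PANSS trigger acts before the 6-month primary end point, so transfers made under it reduce the treatment contrast between arms at that end point. Compliance with allocation is one of the trial's objectives, and the rate of crossover is something a definitive trial has to plan for. If that rate partly reflects which wording a site followed, it is a poorer guide. The rule also bears on safety handling.

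**Working it through.** **Inputs from the protocol.** There are 30 participants per condition (Sampling and Feasibility of recruitment) and two monotherapy arms, so 30 × 2 = 60 participants come under the rule. The threshold is above 12.5%. It is stipulated without derivation, so there is no planned figure to reproduce. The PANSS has 30 items.

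**Step 1: the statements side by side.**

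| Event | Summary of Research | Procedures for deterioration, opening sentence | Procedures for deterioration, list |
|---|---|---|---|
| Hospital admission | Any admission: offer | Offer, if the mental state has deteriorated | Involuntary and due to deterioration: move. Other admissions not named |
| Ideation carrying immediate risk | Offer | Offer, if the mental state has deteriorated | Not named |
| Worsening at 3 months | Offer, no threshold | Offer, no threshold, at any time | PANSS worse by more than 12.5%: move |

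For the two listed events, the first two columns say offer and the last says move. An admission or an episode of ideation that does not reflect a deteriorating mental state is a trigger in the Summary of Research and nowhere in Procedures for deterioration. Abbreviation does not explain this, because the summary is the broader of the two.

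**Step 2: the percentage.** Assume that the score is the PANSS total, that the reference is baseline, and that each item has a minimum of 1, so that the floor is 30. The protocol states none of these for the trigger. Two readings are then possible:

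- raw: (3-month score − baseline) / baseline > 0.125, so the rise must exceed 0.125 × baseline;
- minimum removed: (3-month score − baseline) / (baseline − 30) > 0.125, so the rise must exceed 0.125 × (baseline − 30).

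| Assumed baseline | Raw limit | Smallest whole-point rise | Limit with minimum removed | Smallest whole-point rise |
|---|---|---|---|---|
| 60 | 7.5 | 8 | 3.75 | 4 |
| 70 | 8.75 | 9 | 5.0 | 6 |
| 80 | 10.0 | 11 | 6.25 | 7 |
| 90 | 11.25 | 12 | 7.5 | 8 |
| 100 | 12.5 | 13 | 8.75 | 9 |

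The readings differ by 3 or 4 points throughout. At a baseline of 80, a rise of 7 to 10 points triggers transfer under one and not under the other.

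**Step 3: can the number of transfers be sized?** Only loosely. Put all 60 participants at one baseline and treat change as normal, so that the expected number is 60 × P(change > limit). With baseline 80 and a change SD of 15:

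- no mean change: 60 × 0.252 = 15.1 raw, and 60 × 0.338 = 20.3 with the minimum removed;
- mean improvement of 10 points: 60 × 0.091 = 5.5 raw, and 60 × 0.139 = 8.4 with the minimum removed.

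Over baselines 70 to 90, SDs of 10 to 20, and mean change of zero or a 10-point improvement, the raw reading gives 1.0 to 19.9 and the other 2.4 to 24.1. The protocol supplies no baseline mean, SD or expected change. The direction is stable, since the second reading triggers more in every scenario, but no single count is supportable.

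**The case against.** The strongest reply is that Procedures for deterioration can be read as two tiers: an offer on any deterioration in mental state, and a move on two specified events. On that reading many voluntary admissions and episodes of suicidal ideation fall within the opening offer. This stands, and it narrows the point. A reader might infer that such events trigger transfer in one section and never in the other, but the text does not support that. What survives is the verb for the two listed events, together with admissions or ideation that occur without deterioration.

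A reader might also infer that sites will in fact diverge. The protocol does not show this. Under Communication within and between sites, one trial manager supervises all research assistants weekly, including on scoring queries, and chairs a fortnightly cross-site reliability call. A formula could be settled there or in an operating procedure not shown. Divergence is possible, not established, and central supervision does not remove a conflict in the protocol's own wording.

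On the percentage, total score against baseline is the natural reading, and nothing in the protocol mentions subtracting a scale minimum. That part is a gap in definition, not a contradiction.

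Finally, this is a feasibility trial without hypothesis testing, no progression criterion counts transfers, clinicians' options are unrestricted, and adverse incidents are handled case by case. These facts limit the consequences. They do not tell staff whether to offer or to move. Nor can the matter be left to an analysis plan, because the rule is applied to participants while the trial runs.

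**Conclusion.** The concern holds as an inconsistency that should be fixed. For involuntary admission due to deterioration, and for PANSS worsening at 3 months, the protocol says both that transfer is offered and that it is made. Its detailed section does not name the ideation trigger, or admissions that are not involuntary, which the summary includes. The PANSS percentage lacks a named score, a reference visit and a rule for the scale minimum. Under the assumptions of Step 2, the last omission alone is worth 3 or 4 points in the trigger.

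The inconsistency reaches roughly 60 of the 90 participants. It bears on safety handling, on separation of the arms, and on the crossover rate carried forward. Only the PANSS trigger is tied to 3 months; an involuntary admission can occur at any time. A reader might infer that the analysis set is compromised. It is not: participants remain in the trial, follow-up continues whatever treatment they receive, and analysis is by intention to treat. What is affected is how much combined treatment the monotherapy arms receive, and how the between-arm estimates and adherence figures are read.

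**What to change.** Reconcile the Summary of Research and Procedures for deterioration so that both carry the same list of triggers and the same verb. The clinical content is for the clinical leads to decide. If two tiers are intended, say so in both places.

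In the PANSS trigger, name the score, the reference visit and the percentage formula, including whether the scale minimum is subtracted first.

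Record the date and trigger of every transfer, and report transfers by randomised arm as a feasibility result. Use of medication and psychological therapy is already recorded, so the new item is a transfer field.

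The cost is a protocol clarification and one addition to the case report form. The planned analysis does not change.
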